5. LIST OF ABBREVIATIONS

ACTG	AIDS Clinical Trials Group
AE	Adverse Event
AER	Adverse Event Reports
AIDS	Acquired Immunodeficiency Syndrome
ART	Antiretroviral Therapy
AVRC	Antiviral Research Center
CB	Clinical Investigation and Biostatistics (CB) Core
CD4	CD4 lymphocytes
CFAR	Center for AIDS Research
CMV	Cytomegalovirus
CRF	Case Report Form
ddPCR	droplet digital PCR
DSMB	Data Safety and Monitoring Board
EDI	Estimated date of infection
HBsAg	Hepatitis B surface Antigen
HCV	Hepatitis C Virus
HHV	Human Herpesviruses
HIV-1	Human Immuno-deficiency Virus – 1
HDACi	Histone Deacetylase Inhibitors
HPV	Human Papilloma Virus
HRPP	Human Research Protections Program
HRSA	Health Resources and Services Administration
IL	Interleukin
LPS	Lipopolysaccharide
MMR	Measles, Mumps, Rubella

MSM	Men who have sex with men
NA	not applicable
RCT	Randomized Controlled Trial
RT-PCR	Real Time-PCR
PBMC	Peripheral Blood Mononuclear Cells
PCR	Polymerase Chain Reaction
PID	Participant Identifier
SAE	Severe Adverse Reaction
SCA	Single Copy Assay
SDPIRC	San Diego Primary HIV Infection Consortium
TDAP	Tetanus, Diphtheria and Pertussis
UCSD	University of California San Diego
VZV	Varicella Zoster Virus

6. PROTOCOL SUMMARY

Title: Perturbing the HIV Reservoir

Sample Size: 56

Study Population: HIV-infected individuals between 18 and 65 years old who started antiretroviral therapy (ART) during chronic infection (at least one year from estimated date of infection) and remained virally suppressed for at least 48 weeks before enrollment. Participants will have CD4 >250 cells/ μ l at enrollment and a CD4 nadir >100 cells/ μ l.

Participating Sites: UCSD's Antiviral Research Center (AVRC)

Study Design: The proposed study is a randomized double-blinded controlled trial conducted over 28 weeks. Randomized interventions will be injections of Influenza vaccine, Pneumococcal vaccine, and Placebo. Each participant will receive each injection but in a randomized order. See Figure 1 below.

Schedule of Evaluations: Study evaluations will be based on three 30 day cycles (Influenza vaccine, Pneumococcus vaccine, Placebo in random order) over 28 weeks of the RCT. *Pre injection:* one paired blood, optional stool and optional genital secretion sample will be collected before each injection. *Post-injection:* Blood will be collected on days 2, 4 and 7 while paired blood and optional genital secretion samples will be collected on days 14 and 30 after each injection.

Table 1. Perturb Study - Schedule of Evaluations																				
Activity	Screening	Cycle 1 Treatment Period Fluarix/Fluzone, Pneumovax 23 or Placebo ^a						Cycle 2 Treatment Period Fluarix/Fluzone, Pneumovax 23 or Placebo ^c						Cycle 3 Treatment Period Fluarix/Fluzone, Pneumovax 23 or Placebo ^c						Premature Discontinuation
		Baseline (Day 0)	Day 2 ^b	Day 4 ^b	Day 7 ^b	Day 14 ^b	Day 30 ^b	Week 12 (Day 0)	Day 2 ^b	Day 4 ^b	Day 7 ^b	Day 14 ^b	Day 30 ^b	Week 24 (Day 0)	Day 2 ^b	Day 4 ^b	Day 7 ^b	Day 14 ^b	Day 30 ^b	
Informed Consent	X																			
Eligibility Checklist	X																			
Medical Release	X																			
Vaccination History	X																			
Randomization	X																			
Blood collection ^d		X	X	X	X	X	X	X	X	X	X	X	X	X	X	X	X	X	X	X
Pregnancy test ^e	X																			
Physical Exam		X	X	X	X	X	X	X	X	X	X	X	X	X	X	X	X	X	X	X
Medical History, Health Survey	X	X	X	X	X	X	X	X	X	X	X	X	X	X	X	X	X	X	X	X
Concomitant Medications		X	X	X	X	X	X	X	X	X	X	X	X	X	X	X	X	X	X	X
ARV Adherence		X	X	X	X	X	X	X	X	X	X	X	X	X	X	X	X	X	X	X
Post-vax Symptoms		X	X	X	X	X	X		X	X	X	X	X		X	X	X	X	X	X
Adverse Events		X	X	X	X	X	X	X	X	X	X	X	X	X	X	X	X	X	X	X
Study Drug Injection		X						X						X						
Optional Stool Collection		X						X						X						
Optional Genital Secretion ^d		X				X	X	X				X	X	X				X	X	X
Hematology/Chemistry/Coagulation Panel		X				X	X	X				X	X	X				X	X	X
Immune responses		X	X	X	X	X	X	X	X	X	X	X	X	X	X	X	X	X	X	X
HIV-1 RNA sequencing		X	X	X	X	X	X	X	X	X	X	X	X	X	X	X	X	X	X	X
CD4+ T-cell Count		X	X	X	X	X	X	X	X	X	X	X	X	X	X	X	X	X	X	X
HIV-1 DNA sequencing		X	X	X	X	X	X	X	X	X	X	X	X	X	X	X	X	X	X	X
Archive Plasma		X	X	X	X	X	X	X	X	X	X	X	X	X	X	X	X	X	X	X

- Cycle 1 to begin within 30 days of screening visit
- ± 2 days
- Minimum 6 week washout period between cycles
- Paired blood and optional genital secretion sample will be collected **before** each injection
- Pregnancy Test will be repeated only if pregnancy is suspected.

Study Duration: 240 weeks

[figure not shown]
Study Regimen/Intervention: This is a double blind RCT of two vaccines (Pneumovax®23 and Fluarix® or Fluzone®) plus placebo (sterile saline injection). Study participants will be followed for 28 weeks after enrollment. During this 28-week period, blood samples will be collected on day 0 and five subsequent time points after each injection (days 2, 4, 7, 14 and 30). Optional genital secretion samples will be collected on day zero and on days 14 and 30 after each injection. Optional stool will be collected at day zero. Injections (vaccine or placebo) will be administered 12 weeks apart and in a random order, to minimize a possible bias due to the order of the vaccines.

NOTE: Fluarix® quadravalent vaccine is the flu vaccine of choice for this study. Fluzone® quadravalent vaccine may be substituted for Fluarix® only in the event that Fluarix® is unobtainable from the wholesaler/manufacturer.

Primary Objective: To determine the impact of Pneumococcus and Influenza vaccines on the HIV transcriptional activity in individuals who are virologically suppressed for at least 48 weeks on ART.

Primary Outcome: Average change in level of CD4+ T-cell-associated HIV RNA transcription from baseline to day 7 after each injection.

Figure 1. Study Design and sampling

7. INTRODUCTION

7.1 Background Information

7.1.1 HIV cure strategies

HIV can be effectively treated, but not cured, except for very rare and special circumstances [5]. The recent report of the 'Berlin Patient' [6] has sparked new enthusiasm for such efforts. The first problem with curing HIV is that the virus has a latent stage that persists indefinitely, even during suppressive ART, resulting in recurrence of plasma viremia if ART is stopped. The second problem is identification of specific cells that are latently infected [5]. Most current curative strategies have focused on developing methods that are able to induce the virus from latently infected cells during ART, so that viral proteins are revealed and allow these cellular reservoirs to be cleared by the host immune response, while ART prevents new cells from being infected [7, 8]. Unfortunately, recent interventions to perturb the reservoir, like histone deacetylase inhibitors (HDACi), IL-7, and disulfiram, have demonstrated only modest activity [7, 9-13]. It is also becoming increasingly apparent that it is not enough to just induce HIV RNA expression during ART to clear latently infected cells, but activation of HIV-specific immune responses is also needed [7, 8]. Therefore, it seems likely that parallel efforts to augment the HIV-specific immune response may be required [8, 10, 14]. This proposal aims to evaluate two clinically indicated vaccines with longstanding safety records as immune stimulatory methods for perturbing the HIV reservoir and inducing release of virus and the subsequent potential for viral clearance by the activated host immune system.

7.1.2 Vaccines can stimulate the immune system and HIV reservoir

T-cell activation has been shown to effectively reactivate HIV replication in various *in vitro* models [13, 15-17]. Similar effects have been observed with *in vivo* immune activation secondary to current illness [18-26], human herpesvirus (HHV) shedding [27-30] and gut microbial translocation [31-34]. Prophylactic vaccination represents another means of activating the immune system and has been associated with mostly transient increases in levels of cell-free HIV RNA after vaccination for influenza [21, 35-43], pneumococcus [44-46], tetanus [42, 47], hepatitis B [48] and cholera [49]. This stimulation of the immune system and the HIV reservoir probably occurs because standard clinical vaccines activate not only the small subset of antigen specific cells within the lymphocyte population but also induce a bystander activation of non-specific cells. This hypothesis is supported by the measurable increases in various markers of systemic inflammation (e.g. pro-inflammatory cytokines [interleukin (IL)-6, IL-1, C reactive protein, tumor necrosis factor (TNF)], T-cell activation [CD38⁺HLA-DR⁺] and proliferation [Ki67⁺]) [50-55] after vaccination. For inactivated vaccines, this inflammation is largely mediated by an adjuvant. Studies of vaccine-associated effects on HIV RNA are mixed however, with several studies demonstrating no significant effect on plasma viral loads (i.e., influenza [56-61], pneumococcus [62-64], tetanus [65], hepatitis A [66, 67], hepatitis B [68], measles/mumps/rubella (MMR) [69], *Haemophilus influenzae* type b [70] and yellow fever [71]). The inconsistent findings in the literature are likely secondary to [72-74]: (1) observational convenience studies with varying sampling times (e.g. 1 week versus 1 month), (2) heterogeneous study populations (e.g. different ART regimens, durations of infection, baseline viral loads and CD4⁺ T cell counts [36]), and (3) insensitive methods applied to measure how much HIV RNA is being induced from infected cells. The proposed study will attempt to address these issues by: (1) performing a randomized, double-blind, placebo-controlled trial (RCT) (vaccine vs. vaccine placebo) with optimized sampling times post-vaccination, (2) investigating

participants who have received ART for at least 48 weeks, which was started during chronic infection, and (3) using more sensitive methods to measure virus production from cells (single copy assays to measure cell-free HIV RNA and droplet digital PCR (ddPCR) for cell-associated HIV RNA [75].

While no previous study has examined the impact of vaccines on the HIV reservoir, one Spanish RCT of seven vaccines [1] in chronically infected individuals receiving ART did evaluate the hypothesis that transitory increases in HIV replication during ART would strengthen specific responses against HIV and induce a better control of HIV replication after ART interruption. Although increases in HIV-specific T-cell responses and in T-cell activation were observed in the vaccine group compared to the placebo group, interruption of ART was not associated with control of HIV replication. While this study did not show a significant increase in levels of cell-free HIV RNA production in the vaccine vs. placebo arms, it did suggest that enough HIV transcription was induced to increase HIV-specific immune responses. In contrast to the proposed study, this Spanish study only used standard viral load measures at wide intervals (30 days post-injection)[1]. To further evaluate this hypothesis, we generated preliminary data from the Spanish study [1] using more appropriate assays in support of our hypothesis that vaccination can activate proviruses during ART more than any published HDACi compound [7, 9, 12, 13, 76]. In these experiments, we found (see Figure 2 below):

- no difference in cellular HIV RNA levels between vaccine and placebo groups at baseline ($p > 0.1$),
- significant increases in HIV transcription following each vaccine (all $p < 0.05$),
- mean fold change in cell-associated HIV RNA *gag* transcripts following both Influenza and Pneumococcal vaccines was considerably higher than what has been observed in two clinical studies of the HDACi Vorinostat (Archin et al.[3] and Elliott et al.[4]).

In summary, we acknowledge that the literature is not clear whether or not clinical vaccination can perturb the HIV reservoir, but this is because all previous studies:

- Were observational with a very wide range of sampling times (<1 week to >1 month).

7.1.3 Vaccines for HIV-infected people

HIV-infected individuals are at increased risk for a variety of communicable diseases compared to uninfected people and several vaccines are routinely recommended. In general, vaccines have better efficacy in HIV-infected individuals with CD4 counts >200 cells/ μ L [77]. However, all vaccines are not created equal [78]. They can differ in immune stimulating mechanism; some induce mostly neutralizing antibodies while others also induce cytotoxic T-cell responses [78-86]. They can also differ in efficacy; for example the human papilloma virus (HPV) vaccine is close to 100% effective while influenza is only ~65% effective [87]. Further, immune responses wane over time and at different rates; the tetanus vaccine requires repeat vaccination every 10 years, while the protection from the smallpox vaccine is likely life-long [87]. Additionally, effective inactivated vaccines often require an adjuvant (Alum, AS04, or MF59), which primes the innate and adaptive immune responses quite differently [78]. This study will evaluate the two standard vaccines that showed the greatest mean increase in HIV RNA transcription following vaccination in the Spanish Trial (see Research Plan). Other vaccines could be evaluated in this proposal, but we chose the Influenza and Pneumococcal vaccines that are commonly used clinically and have a very long safety record.

7.1.4 Incidental Immune Stimulation

Immune stimulation following vaccination has the potential to be confounded by immune activation associated with other specific and non-specific stimuli [28, 88-90]. In an effort to

optimally control for possible confounding within a relatively small RCT, we propose a detailed analysis of the possible contribution of incidental immune stimulation resulting from HHV infections, microbial translocation, drug use and clinical illnesses. For example, we recently showed that CMV replication in seminal plasma of HIV infected subjects on suppressive ART was associated with increased levels of T-cell activation and higher levels of proviral HIV DNA and cellular HIV RNA compared to subjects with no detectable CMV (Figure 2) [30]. Additionally, our group has identified an association between methamphetamine use and increases in both immune activation and HIV DNA levels during suppressive ART [91]. Therefore, we will try to identify these factors and account for their potential effect. Specifically, we will identify and measure: 1) genital shedding of 7 HHV (by RT-PCR), 2) microbial translocation (as measured by lipopolysaccharide [LPS], bacterial 16s rDNA and soluble [s]CD14), 3) active or recent illicit substance use (using validated questionnaires [92-94] and urine toxicology) and 4) recent clinical illnesses (e.g. colds, skin infections, sexually transmitted infections) and clinical events (e.g. surgeries).

7.2 Rationale

Most recent HIV cure efforts have focused on strategies to induce virus from latently infected cells during ART, thus leaving the cellular reservoir vulnerable to the host immune system, while ART prevents new cells from being infected. Unfortunately, such efforts have not demonstrated much activity. On the other hand, it has been documented for almost two decades that routine clinical vaccines can induce viral production from latently infected cells, even during ART, and that these levels of induction are much higher than those seen by recently described interventions (e.g. histone deacetylase inhibitors (HDACi), IL-7, disulfiram). Therefore, we propose a RCT with cross-over to determine how two commonly used vaccines (Influenza and Pneumococcus) can stimulate the immune system and induce HIV transcription. In preliminary data, these vaccines demonstrate a higher cell associated HIV RNA transcriptional response even 30 days after vaccination than the HDACi Vorinostat; see Figure 2. In this proposal, we will use a much safer method (vaccination with Influenza and Pneumococcus) and observe timepoints much closer to the time of vaccination to tease out how immune stimulation perturbs the HIV DNA reservoir suppressed by ART.

Rationale for measuring total and replication competent HIV DNA

Currently, much emphasis has been placed on the kick portion of the kick-and-kill HIV cure strategy; however, only modest benefit has been seen with kick interventions and almost none with the killing of infected cells- at least with the current measurements in circulating blood [7, 9-13]. In this study, we will use clinically available influenza and pneumococcus vaccines to stimulate the HIV reservoir and stimulate the immune response. In the prior Spanish Study, described in the Background, it was observed that HIV-specific immune response was enhanced during the 'kick' of the reservoir in the blood after a clinical vaccine. This study did not measure HIV DNA levels or replication competent proviral levels; therefore, we do not know if this HIV-specific immune stimulation had an impact on the HIV reservoir in circulating blood cells. Therefore, in the proposed RCT, we will assess both total HIV DNA levels and replication competent provirus (using an "inducible RNA assay" [95]) among the five participants with the highest cell associated HIV RNA response to the vaccine intervention.

Microbiome Composition

Infection with HIV is associated with dramatic alterations in the gut-associated lymphoid tissue, which occur early in the course of infection and contribute to persistent immune dysfunction and HIV disease progression. Mucosal HIV replication and consequent depletion of gut-associated CD4⁺ T cells is associated with epithelial barrier damage and increased translocation of bacterial products from the gut lumen into the systemic blood circulation (i.e. microbial translocation). In turn, microbial translocation is associated with systemic immune activation and might play a role in immune response and disease progression in untreated and treated HIV infected individuals.

As part of this study we will determine the effect of the intestinal microbiome composition on the viral and immunologic dynamics before and after vaccine administration.

7.3 Major Hypotheses

(All hypotheses are presented “under the alternative”)

Primary Hypothesis:

On average, participants will have a higher absolute increase in levels of cell-associated HIV RNA transcription in CD4⁺ T-cells seven days after receiving either Pneumococcal or Influenza vaccinations, when compared to seven days after receiving placebo.

Secondary Hypotheses:

- Among the five participants with the largest increases in cell-associated HIV RNA in CD4⁺ T-cells following active vaccination (maximum across all observed time-points), we will deep sequence cell-associated HIV RNA and DNA populations at 0, 2, 4, 7, 14 and 30 days. We hypothesize that active vaccines will *non-selectively* activate cellular transcription of HIV, as evaluated by panmixis tests between sequences of HIV DNA and RNA populations at these sampled timepoints.
- On average, participants will have a greater absolute maximum decrease in levels of total CD4⁺ T-cell-associated HIV DNA measured 2-30 days after receiving either Pneumococcal or Influenza vaccinations, when compared to 2-30 days after receiving placebo.
- Among the five participants with the largest increases in cell-associated HIV RNA in CD4⁺ T-cells following active vaccination (maximum across all observed time-points), we will perform inducible RNA assay. We hypothesize that these five participants will have lower levels of replication competent proviruses 30 days after active vaccination, as compared to their levels of replication competent proviruses sampled before this vaccination.
- Participants will have a greater absolute maximum increase in levels of (a) inflammatory cytokines, (b) T-cell activation and proliferation, (c) HIV-specific immune responses, and (d) vaccine-specific immune responses over the 30 days of observation after receiving either active vaccination, when compared to maximum measures taken over the 30 days of observation after receiving placebo.

- Levels of non-antigen specific immune stimulation (cytokines and general T-cell activation) and vaccine-specific immune responses will be positively associated with increased CD4⁺ T-cell-associated HIV RNA transcription and negatively associated with lower levels of HIV DNA, over the 30 days of observation after receiving either Pneumococcal or Influenza vaccinations.
- Maximum levels of cell-associated HIV RNA over the 30 days of observation following active vaccination will be positively associated with HIV-specific responses 30 days after receiving active vaccinations.
- Genital shedding of human herpesviruses, increased levels of microbial translocation and incident illnesses will stimulate the immune system and induce increased cell-associated HIV RNA transcription from CD4⁺ T-cells in participants independent of receiving active vaccine or placebo.
- Presence of dysbiosis (for example increased relative frequency of Proteobacteria in stool samples) will be associated with increased microbial translocation and with increased cell-associated HIV RNA transcription from CD4⁺ T-cells in participants independent of receiving active vaccine or placebo.

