8.2.2 Aim 1b

Determine if vaccination selectively or non-selectively activates HIV transcription from HIV DNA populations

8.2.3 Aim 2

Determine if active vaccination influences levels of cell associated HIV DNA or replication competent provirus.

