12.2 Laboratory Evaluations

All laboratory procedures will be conducted in accordance with Good Clinical Laboratory Practices (GCLP) according to the [DAIDS guidelines](#).

A urine pregnancy test will be performed at screening in women who can become pregnant and will be repeated only if pregnancy is suspected.

A rapid HIV test will be performed if no documentation of previous HIV infection is provided.

Table 3 is a summary table of study assays, methods and time points.

	Measurements	Methods	Sample	Sampled Time-points (Days)
Virologic (Aims 1+2)	Cell-associated HIV RNA levels	(dd)PCR	PBMC (CD4+)	
	HIV DNA levels (pol and 2-LTR)	(dd)PCR	PBMC (CD4+)	0, 2, 4, 7, 14, 30 after each injection
	Cell-free HIV RNA levels	SCA	Blood plasma	
	Cell-associated HIV RNA diversity*	env NGS	PBMC (CD4+)	0 and time point with highest cell associated HIV RNA level after the active vaccination
	Cell-associated HIV DNA diversity*	env NGS	PBMC (CD4+)	
	Replication competent HIV levels*	DNA Inducible RNA assay	PBMC (CD4+)	0 and 30 after each active vaccine
Immunologic	Soluble inflammation markers	ELISA	Blood plasma	0, 2, 4, 7, 14, 30 after each injection

(Aim 3)	Vaccine-specific response	ELISA	Blood plasma	
	Cellular inflammation markers	Flow	PBMC	
	HIV-specific T-cell response	Flow ICC	PBMC	
Incidental stimulation	Microbiome Composition	r16s Sequencing	Stool	Day 0
	HHV quantification	qRT-PCR	GS	0, 14, 30 after each injection
	Incident Illness surveys	Survey	--	

Legend: ddPCR: digital droplet PCR, SCA: single copy assay, PBMC: peripheral blood mononuclear cells, ELISA: enzyme linked immunoassay, Flow: flow cytometry, ICC: intracellular cytokine staining, qRT-PCR: quantitative real time PCR. GS: genital secretion. *The 5 participants with the highest sum levels of cell-associated HIV RNA within the 30 days (five measures) following both active vaccinations will undergo these assessments. These same 5 participants will be used for both of these analyses.

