15.2 Study Endpoints

15.2.1 Primary Endpoint

Average change in level of CD4+ T-cell-associated HIV RNA transcription from baseline to 7 days after each injection.

15.2.2 Secondary Endpoints:

1. Average change in level of CD4+ T-cell-associated HIV RNA transcription from baseline to 2, 4, 14 and 30 days after each injection.
2. Average change in levels of HIV DNA from baseline to 2, 4, 7, 14 and 30 days after each injection.
3. Determine selective vs. nonselective HIV RNA production from HIV DNA (by next generation sequencing and panmixis tests) among the five participants with the highest levels of cell associated HIV RNA following active vaccination.
4. Average change in levels of immune activation (soluble and cellular markers) from baseline to 2, 4, 7, 14 and 30 days after each injection.
5. Average change in levels of replication competent HIV DNA (by inducible RNA assay) among the five participants with the highest levels of cell associated HIV RNA following active vaccination.
6. Average change in levels of HIV specific T-cell immune response from baseline to 30 days after each injection.
7. Stimulation of HIV transcription by incidental illness, human herpesviruses replication and microbial translocation over the course of the study.
8. Possible immunomodulatory effect of microbiome composition
9. Vaccine administration will be safe for all included participants.

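### Aim 1b names as its alternative hypothesis what is the null of the panmixis test, so only a non-significant result can agree with it, and that result alone cannot show non-selective activation

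*Combined protocol and SAP*

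**What the plan says.** Section 7.3 states that "All hypotheses are presented" under the alternative. Its first secondary hypothesis, which serves Aim 1b, says: "We hypothesize that active vaccines will *non-selectively* activate cellular transcription of HIV", and this is to be judged "as evaluated by panmixis tests between sequences of HIV DNA and RNA populations at these sampled timepoints". It concerns the five participants with the largest rise in cell-associated HIV RNA, of whom 7.3 says "we will deep sequence cell-associated HIV RNA and DNA populations at 0, 2, 4, 7, 14 and 30 days".

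The objective in 8.2.2 is worded neutrally: "Determine if vaccination selectively or non-selectively activates HIV transcription from HIV DNA populations". So is secondary endpoint 3 in 15.2.2: "Determine selective vs. nonselective HIV RNA production from HIV DNA (by next generation sequencing and panmixis tests) among the five participants". Table 3 in 12.2 assigns the sequencing to "The 5 participants with the highest sum levels of cell-associated HIV RNA within the 30 days (five measures) following both active vaccinations", but lists only day 0 and the sample with the highest cell-associated RNA after active vaccination.

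Section 15.4 gives power examples for HIV RNA, HIV DNA and T-cell activation, and none for Aim 1b. Section 15.8.2 sets alpha for the two primary tests only, and refers additional analyses to a Statistical Analysis Plan. I found no SAP text on the panmixis tests in the combined document.

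**The concern.** Panmixis means one freely mixed population. A test of it starts from the position that RNA and DNA sequences are draws from the same population, and a rejection shows structure between them, that is, selective transcription. The hypothesis that 7.3 labels an alternative is thus the position the test starts from. Data can contradict it but cannot establish it through this test.

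The claim at stake is that vaccination reaches the whole transcribable reservoir and not just a few lineages. Under the plan's wording, poorer sequence recovery makes agreement with that claim more likely.

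**Working it through.** **Step 1: hypothesis against test.** No arithmetic is needed here.

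| | Section 7.3 | Panmixis test |
|---|---|---|
| Non-selective (RNA and DNA form one population) | Stated as the alternative | Null |
| Selective (RNA and DNA differ) | Not stated | Alternative |
| Result agreeing with 7.3 | | Non-rejection only |

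The documents do not write out the panmixis null; it follows from what the test is. Sections 8.2.2 and 15.2.2 are neutral on direction but do not change the test or add a rule for reading it.

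**Step 2: is there a plan figure to reproduce?** No. The text gives no power, alpha, sequence count or tolerance for this aim. Everything in steps 3 to 5 is illustration on stated assumptions.

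**Step 3: what non-rejection in five people can mean.** Assume activation is truly selective, with one independent test per person and power *p* for each. Then P(no rejection in five) = (1 − *p*)^5, and P(three or more non-significant) is the binomial tail with n = 5 and miss probability 1 − *p*.

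| Assumed *p* | None of five rejects | Three or more non-significant |
|---|---|---|
| 20% | 0.8^5 = 33% | 94% |
| 40% | 0.6^5 = 7.8% | 68% |
| 60% | 0.4^5 = 1.0% | 32% |
| 80% | 0.2^5 = 0.03% | 6% |

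Both the power range and the three-of-five threshold are assumptions; neither is in the plan. If none of five rejects, the one-sided 95% upper bound on the share of such people in whom the test would reject is 1 − 0.05^(1/5) = 45%.

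**Step 4: power depends on sequence numbers.** An illustrative simulation took ten equal lineages in DNA, with 20% of RNA diverted to one lineage, whose RNA share becomes 0.8 × 10% + 20% = 28%. It drew equal numbers of DNA and RNA sequences per person and applied a label-permutation test at 0.05 (400 data sets, 199 permutations each).

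| Sequences of each type | Power per person | All five miss it |
|---|---|---|
| 10 | 11% | 57% |
| 20 | 12% | 54% |
| 50 | 27% | 21% |
| 100 | 62% | 1% |

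The Monte Carlo standard error of the power is at most √(0.615 × 0.385/400) = 2.4 percentage points. With 100 sequences, power is 21% if only 10% of RNA is diverted and 92.5% if 30% is. The same biological selectivity therefore gives opposite readings depending on recovery, which the plan does not state.

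**Step 5: the opposite error.** For any fixed non-zero difference, power tends to 1 as sequence counts grow, so a very large data set can reject over a difference of no interest. Repeated testing pushes the same way. Under true non-selectivity, with five independent tests at an assumed 0.05, at least one rejects with probability 1 − 0.95^5 = 22.6%.

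**Step 6: time points.** Section 7.3 sequences days 0, 2, 4, 7, 14 and 30 (six samples). Table 3 sequences day 0 and the peak sample (two). The number of tests is not settled.

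**The case against.** A reader might infer that the plan will declare non-selectivity whenever the test is non-significant. No section says so. Section 7.3 says only that the hypothesis is evaluated by the test, and the objective and endpoint are neutral, so a rejection would also answer Aim 1b. What stands is that the rule for interpretation is missing.

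A reader might also infer that five participants make the test underpowered. The documents do not support that. Power within a person depends on the number and diversity of sequences. The plan uses deep sequencing in participants chosen for high cell-associated RNA, which works against scarcity without guaranteeing adequate counts. Having five people mainly limits how far the result generalises.

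The 94% figure should not be quoted as the size of the problem, because the same calculation runs down to 6% across the assumed range.

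The SAP cited in 15.8.2 may hold a decision rule, so statements about what is missing apply to the text available here. Finally, this is one secondary endpoint with no power claim attached, and a descriptive label would also remove the difficulty.

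None of this answers the reversal itself: the hypothesis labelled as the alternative is the null of the only test named for it.

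**Conclusion.** The point holds as a mismatch between hypothesis and test. On the panmixis result alone, non-selectivity cannot be told apart from too few sequences, and a rejection cannot be told apart from a trivial difference found in a very large data set. This rests on the wording of 7.3 and on the standard meaning of a panmixis test, and needs no assumption about power.

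The size of the consequence is not established. It turns on sequence counts and on the degree of selectivity, neither of which the available text states. Low power is a risk, and the tables only show how strongly the reading depends on it. The primary analysis, sample size and safety monitoring are unaffected. The text should be corrected before sequencing begins.

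**What to change.** In 7.3 and in 15.2.2 item 3:

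- State the panmixis null (RNA and DNA sequences form one population) and the alternative (they differ).
- Report for each participant a named RNA-versus-DNA differentiation measure with a 95% interval at each sequenced time point, and its change from Day 0. Fst or the proportion of shared haplotypes would serve.
- State that a non-significant panmixis test alone is inconclusive.
- Allow the conclusion of non-selectivity only if a tolerance was fixed and justified before sequencing and the upper limit of the interval lies below it. If no tolerance can be justified, label the aim descriptive.
- Reconcile the sequencing time points in 7.3 (days 0, 2, 4, 7, 14 and 30) with those in Table 3 (day 0 and peak).

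If the SAP already contains such a rule, 7.3 and 15.2.2 should point to it. The cost is wording plus a small additional analysis of the same sequences, with no new samples. The downside is that the aim may end up reported as inconclusive.
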